Cover Page for Protocol

Sponsor-Investigator:	[name]
NCT Number:	NCT03597568
Unique Protocol ID:	201806073
Official Title:	Effect of resveratrol on endothelial function in patients with CKD and diabetes: A randomized controlled trial
Document Date:	23 February 2024

Background and significance

Patients with chronic kidney disease (CKD) have an exceptionally high risk for cardiovascular disease (CVD) and are 10 times more likely to die from CVD prior to requiring dialysis or kidney transplantation (1). Multiple studies have shown CKD to be an independent risk factor for cardiovascular events and mortality (2-6). Diabetes mellitus is the most common cause of CKD and is believed to contribute to a significant portion of the CVD with CKD (7). Indeed, patients with CKD and diabetes have a disproportionately higher risk for CVD when compared with patients with diabetes who do not have CKD (8). Thus, it is paramount that we explore therapies that may ultimately reduce the burden of CVD in those with CKD and diabetes.

Endothelial dysfunction via brachial artery flow mediated dilation (BA-FMD), is a reliable and non-invasive vascular assessment, which has been shown to predict CVD *prospectively* in a wide variety of 'at-risk' and diseased populations, including individuals with CKD (9). Preliminary data by our group demonstrates that endothelial function via BA-FMD test is significantly lower in individuals with CKD and diabetes as compared to those with CKD but without DM (Fig 1). These findings suggest that the etiology of DM within CKD patients appears to exacerbate the condition more so than CKD alone.

Experimental studies, suggest that resveratrol (a widely-available nutraceutical) inhibits inflammation and restores endothelial nitric oxide (NO) *in vitro* (9-11) and *in vivo* (12,13).

In this pilot study, we will evaluate if resveratrol supplementation improves endothelial function and oxidative stress in those with CKD and diabetes.

Study Design

25 subjects with stage 3 CKD and diabetes will be randomized to receive either resveratrol first then matching placebo or placebo first then resveratrol in a randomized cross over study. Resveratrol will be prescribed at 400 mg per day. The treatment with resveratrol or placebo will be for 6 weeks and separated by a 2 week washout period.

The inclusion criteria are shown in Table 1.

Figure 1: Patients with DKD exhibit lower BA-FMD compared to those with CKD without diabetes

[figure not shown]

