Table 1

Inclusion Criteria	Exclusion Criteria
Age 45-80 years old	Consuming >2 glasses/day red wine and/or taking resveratrol or vitamin C supplement in the past 12 months
CKD stage 3 (CKD-EPI eGFR: 30-60 mL/min/1.73m ²) on 2 occasions \geq 3 months apart	Life expectancy <1 year
Type II DM	Pregnant, breastfeeding, or unwilling to use adequate birth control
angiotensin converting enzyme inhibitor or angiotensin II receptor blocker for \geq 3 months prior to the study	Uncontrolled hypertension; blood pressure >140/90
Able to give informed consent	Severe liver disease
	Severe congestive heart failure
	Hospitalization within the last 3 months
	Active infection or antibiotic therapy
	Immunosuppressive therapy within the last year
	Uncontrolled DM with A1C > 8.5
	Currently taking anticoagulants including the following: coumadin, dalteparin, enoxaparin, heparin, and plavix.
	Severe systolic heart failure
	Currently partaking in another research study

Our rational for RSV dose is that: 1) it is available commercially at 400 mg and 2) recent studies utilizing RSV suggest that this dose is safe and does not result in serious side effects (14, 15).

The study is registered with clinicaltrials.gov

Institutional Review Board was obtained. The informed consent will detail the risks associated with the study drug and with all the study procedures.

- **Detailed study sessions**

All study procedures will be conducted at UIHC Clinical Research Unit (CRU) and all experimental testing measurements will be conducted after an overnight fast as well as refraining from exercise and caffeine prior to testing.

Session 1: Informed consent and screening questionnaire for inclusion and exclusion criteria including confirmation of stage 3 CKD on 2 separate occasions in the last 6 months. All women in child-bearing age will undergo pregnancy test at this visit. In addition, all participants will complete a 7-day physical activity recall.

Session 2:

- Blood pressure at rest
- Endothelial cell sampling
- Blood sampling for fasting lipid profile
- Blood sampling for hemoglobin A1C
- Blood sampling for levels of RSV and its metabolites
- Blood sampling for basic metabolic profile and estimated GFR including cystatin C
- Blood sampling for circulating markers of inflammation and oxidative stress (oxLDL)
- Urine sampling (random) for albumin/creatinine ratio (ACR)
- Evaluation of EDD and EID by measurements of BA-FMD and nitroglycerin-mediated dilation (NMD)

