- Start study drug after this visit

Session 3: will include the same measurements as Session 2. In addition, it will include the following:

- Physical activity questionnaire
- Pill count
- Safety monitoring:
 - Completion of an adverse event questionnaire
 - Update medication list

Sessions 4 and 5: will involve the exact same procedures as Sessions 2 & 3 above except it will involve the other study drug being ingested for 6 weeks (resveratrol or placebo).

- **Outcome measurements**

1. Measurements of endothelial dependent and independent dilation: *Endothelial dependent dilation* (EDD) of the brachial artery (BA-FMD) will be measured at the Cardiovascular Research Lab in the Clinical Research Unit (CRU) at the University of Iowa by principal investigator using high-resolution Doppler ultrasonography as described originally by Celermajer et al (16,17). *Electrocardiogram (ECG) gated end-diastolic ultrasound images and Doppler flow of the artery will be acquired during baseline and FMD and conditions.* Briefly, and after 15 minutes of quiet supine rest, the vascular reactivity of the brachial artery will be assessed as based on the following: 1) two minutes of baseline hemodynamics followed by inflation of a rapidly inflating pneumatic pediatric cuff wrapped around the maximal circumference of the forearm to a pressure of 240 mmHg for 5 min, and 2) rapid deflation of the cuff after five minutes. A commercially available software package will be used to acquire and analyze ECG-gated brachial artery diameters. *Endothelial independent dilation (EID) will also be determined by measuring brachial artery dilation for 10 minutes after administration of sublingual nitroglycerin (0.4 mg).* BA-FMD

(pre- vs. post-intervention) will be calculated as the % change from baseline and compared against the placebo condition.

2. Systemic markers of oxidative stress: oxidized low density lipoprotein (LDL) cholesterol (ALPCO Diagnostics, Catalog #30-7810) will be quantified using commercially available enzyme-linked immunosorbent assays performed according to kit instructions.

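### No adverse event or medication enquiry is scheduled at Session 4, so anything starting in the washout is first asked about at the end of the second treatment period

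*Combined protocol and SAP*

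**What the plan says.** Under Study Design, each patient takes resveratrol and placebo for 6 weeks each, in randomised order, "separated by a 2 week washout period".

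Under Detailed study sessions, Session 2 lists resting blood pressure, endothelial cell sampling, blood and urine tests and the vascular measurements, and ends with "Start study drug after this visit". It names no adverse event enquiry and no medication review. Session 3 "will include the same measurements as Session 2. In addition, it will include the following": a physical activity questionnaire, a pill count and two safety items, namely "Completion of an adverse event questionnaire" and "Update medication list". Sessions 4 and 5 "will involve the exact same procedures as Sessions 2 & 3 above"; the one stated difference is that the patient now takes the second of the two treatments, again for 6 weeks.

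The document describes no other route for collecting adverse events. It mentions no contact during the washout, no rule for spontaneous reports, no onset dates and no rule for assigning an event to a treatment or to the washout.

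**The concern.** In a crossover trial, the time between the two treatments is where it is hardest to say which treatment an event belongs to. A late or continuing effect of the first treatment, or a problem following the procedures at Session 3, would show itself in the washout. The schedule passes over Session 4 and next asks at Session 5, when the patient has completed the other treatment. Without an onset date, such an event can only be recorded under the second treatment or missed.

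Two things are at stake. The first is the safety record. In patients who take resveratrol first, a late resveratrol effect could be listed under placebo. Placebo-first patients offer no clear offset, because resveratrol is their last treatment and no session is listed after Session 5. The second is the second-period baseline. Session 4 supplies the pre-treatment BA-FMD for that period, and no medication review is scheduled before it or before the second study drug is started. Table 1 makes several medications a condition of entry, so the plan itself treats medication use as relevant.

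**Working it through.** The plan states no figure on this point, so there is none to reproduce. The check maps sessions to procedures and then follows the timeline.

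**Inputs.** Treatment periods of 6 weeks and a washout of 2 weeks (Study Design); session contents (Detailed study sessions); 25 subjects (Study Design). Assumption: visits fall at the ends of the stated periods, because no visit windows are given.

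**Step 1: mapping.** Session 2 precedes the first study drug and Session 3 follows it. The BA-FMD outcome is defined as pre- versus post-intervention and compared with placebo, so the second period needs the same pair: Session 4 corresponds to Session 2, and Session 5 to Session 3. Reading the sentence as both sets of procedures at both visits is implausible, since Session 4 comes before the second study drug.

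| Session | Week | Place in design | Adverse event questionnaire | Medication update |
|---|---|---|---|---|
| 2 | 0 | before first study drug | no | no |
| 3 | 6 | end of first treatment | yes | yes |
| 4 | 6 + 2 = 8 | end of washout, before second study drug | no | no |
| 5 | 8 + 6 = 14 | end of second treatment | yes | yes |

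**Step 2: delay to enquiry.** For onset at week t in the washout (6 to 8), the delay to Session 5 is 14 − t:
- onset at week 6: 14 − 6 = 8 weeks
- onset at week 8: 14 − 8 = 6 weeks

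With an enquiry at Session 4, the delay is 8 − t, which is 0 to 2 weeks, and it ends before any exposure to the second treatment.

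**Step 3: share of follow-up.** Washout / total = 2 / (6 + 2 + 6) = 2/14 = 14%.

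**Step 4: intervals between enquiries.** Session 3 covers 6 − 0 = 6 weeks. Session 5 covers 14 − 6 = 8 weeks. The ratio is 8/6 = 1.33, and it is a difference between periods.

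**Step 5: does this carry over to treatments?** Assume that all 25 complete follow-up, that the event rate is constant, and that the split is 12/13 (the allocation ratio is not stated), with 13 taking resveratrol second. If each questionnaire's whole interval is assigned to the treatment just finished:
- resveratrol: 13 × 8 + 12 × 6 = 176 person-weeks
- placebo: 12 × 8 + 13 × 6 = 174 person-weeks
- ratio: 176/174 = 1.01

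Background events are therefore almost balanced between treatments.

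**The case against.** The strongest reply is that the consequence is inferred. The questionnaire is named but not shown. It may ask for onset dates, and patients may report events unprompted. The session list is also visibly incomplete: updating a medication list presupposes an initial list that no session names, and urinary resveratrol is an outcome although the sessions mention urine only for the albumin/creatinine ratio. This stands as far as it goes. Loss or misplacement is possible but not shown. It does not remove the scheduling gap, because the plan says what Session 4 contains by reference to Session 2.

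A reader might infer from the 8-week and 6-week intervals that the resveratrol–placebo safety comparison is distorted by a third. The documents do not support this. The excess belongs to the period, and randomised order nearly cancels it between treatments. It also arises only if every washout event is captured at Session 5; events that are lost add nothing to the second period. What randomised order does not settle is the placing of genuinely late drug effects, whose frequency the documents give no means to estimate.

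Three further points are fair. The Statistical analysis section plans no formal comparison of adverse events. Session 4 is not without any check, since it repeats blood pressure, the metabolic profile, eGFR and other laboratory tests, although these do not replace an enquiry about events or medication. The past tense of that section also suggests that the visits may be over.

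**Conclusion.** The point holds as a gap in the visit schedule, with modest consequences. As written, scheduled adverse event and medication enquiry falls only at about weeks 6 and 14, and none precedes the second baseline or the start of the second study drug. An event or medication change in the washout is first asked about 6 to 8 weeks after onset. It may then be missed or recorded under the wrong condition, and late resveratrol effects in resveratrol-first patients could appear under placebo.

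The 14% share gives scale and does not predict a count of misplaced events. These timings rest on visits at period ends. It would go too far to say that washout events are lost, or that the treatment comparison is biased by a known amount. The primary BA-FMD analysis does not use these data and is not directly affected.

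**What to change.** Add the existing adverse event questionnaire and medication-list update to Session 4, completed before the second study drug is started. Record an onset date for each event at Sessions 3, 4 and 5. Tabulate events by period of onset (first treatment, washout, second treatment), with washout-onset events as a separate category broken down by preceding treatment. Folding them into the preceding treatment would only reverse the imbalance, giving 8 weeks to the first period and 6 to the second.

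The cost is an amendment to the session list and a few minutes at a visit that already takes place.

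If the visits are complete, the questionnaire cannot be added. In that case, state whether the two items were in fact collected at Session 4, tabulate events by onset date from existing records where available, and disclose that no enquiry was scheduled at that visit.

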3. Endothelial cell sampling and cell protein expression: This technique will be done by a trained/qualified individual at the UI CRU. Briefly, J-wires will be advanced into an antecubital vein and withdrawn. Cells will be recovered by standard techniques (18). Collected cells will be fixed with 3.7% formaldehyde and plated on slides. After blocking nonspecific binding sites with 5% donkey serum, cells are incubated with the primary antibody and with CY3-conjugated secondary antibodies. Slides will be systematically scanned to identify endothelial cells (positive VE-Cadherin) and nuclear integrity confirmed using 4',6'-diamidino-2-phenylindole hydrochloride staining. Once endothelial cells with intact nuclei are identified, images will be captured and then analyzed to quantify the intensity of CY3 staining (i.e., average pixel intensity). Values for each sample will be reported as ratios of endothelial cell protein expression/human umbilical vein endothelial cell (HUVEC) to account for any variation in the staining procedure. Sirtuin 1 expression will be evaluated since this has been reported to increase with resveratrol.

4. Other measurements: High performance liquid chromatography coupled with tandem mass spectrometry will be used to determine plasma and urine levels of resveratrol and its metabolites. In addition, urinary albumin/creatinine ratio, serum creatinine and estimated GFR will be assessed at the University of Iowa Clinical Lab.

- **Statistical analysis**

Normally distributed data are presented as mean \pm SD, non-normally distributed data as median (interquartile range), and categorical data as count (percentage of patients). To determine the effects of resveratrol supplementation on our primary and secondary outcomes, a generalized linear mixed effects model was used to examine the significance of condition, time, and their interaction for normally distributed variables, and a gamma mixed effects model was used for non-normally distributed variables. In each model, a random intercept was built for each patient to account for inherent between-patient variability. A complete case analysis was utilized when analyzing primary and secondary outcomes. A Wilcoxon Rank Sum Test was used to test differences in resveratrol metabolites between the resveratrol and placebo arms. Significance was set at an alpha level of 0.05. All analyses were performed in R, version 4.2.3 (R Foundation for Statistical Computing, Vienna, Austria).

References

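### The rule that sends non-normal outcomes to a gamma model has no exemption for BA-FMD, a percentage change that can be zero or negative

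*Combined protocol and SAP*

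**What the plan says.** The Statistical analysis section opens its model rule with "To determine the effects of resveratrol supplementation on our primary and secondary outcomes", so the rule covers all of these outcomes. One mixed model is used "to examine the significance of condition, time, and their interaction for normally distributed variables". For the rest, "a gamma mixed effects model was used for non-normally distributed variables". Each model has a random intercept per patient. The only other method named is a rank sum test for resveratrol metabolites. The complete-case sentence deals with missing data. The section gives no normality test, transformation, offset or alternative model, and no rule for values at or below zero.

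Outcome measurements, item 1, says that BA-FMD "will be calculated as the % change from baseline and compared against the placebo condition". The same item uses the word baseline for the resting artery within a test: "two minutes of baseline hemodynamics followed by inflation of a rapidly inflating pneumatic pediatric cuff". Background and significance gives the aim: "we will evaluate if resveratrol supplementation improves endothelial function and oxidative stress in those with CKD and diabetes". Endothelial function comes first in that aim, and BA-FMD is part of the first outcome listed.

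**The concern.** A percentage change is zero or negative whenever the later diameter does not exceed the reference diameter. The rule depends only on the shape of the data, so nothing keeps BA-FMD out of the gamma branch. Four paths are open:

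- BA-FMD judged normal: the Gaussian model is used, and there is no problem.
- Judged non-normal, all values positive: the gamma model can be fitted.
- Judged non-normal, some values at or below zero, those values deleted.
- The same, with all values shifted upwards by a chosen constant.

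The last two are workarounds that the text does not define. Deletion removes the poorest responses selectively. A shift makes the result depend on an arbitrary constant. The section is written in the past tense, yet a reader cannot tell which path produced the BA-FMD result.

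**Working it through.** The plan gives no figure on this point to reproduce. Its text gives no BA-FMD mean, SD or shape, so every mean/SD, shape and correlation below is an assumption. From the plan come 25 patients, four measurement sessions (Sessions 2 to 5, so at most 25 × 4 = 100 values), the model terms and alpha 0.05.

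**1. Which values enter the model.** The condition, time and interaction terms need one value per session. I therefore take baseline to be the resting diameter within the session: BA-FMD = 100 × (peak − resting)/resting.

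**2. Can gamma take such values?** The gamma density is defined only for y > 0. With shape 2 and scale 2, the log-density is −2.33 at y = 0.5 and minus infinity at y = 0 and y = −1. One value of −0.5 among 100 makes the total log-likelihood minus infinity.

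**3. Chance of any value at or below zero.** For normal, independent values, p = Φ(−mean/SD), and the chance of at least one in 100 is 1 − (1 − p)^100.

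| Mean/SD | p | At least one of 100 |
|---|---|---|
| 6/2 | 0.0013 | 13% |
| 4/2 | 0.0228 | 90% |
| 4/3 | 0.0912 | >99.9% |

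With within-patient correlation 0.8 the last column becomes 9%, 74% and 99%. Right skew can remove the problem. A Pearson III shape with skew 1 has lower bound mean − 2 × SD, which is 0 at 5/2.5 and 2 at 6/2, so no value falls below zero there. At 4/3 the bound is −2.

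**4. Chance of both conditions together.** The plan names no normality check. Two were tried, both Shapiro-Wilk at 0.05: one test on all 100 pooled values, and one test on a single session (n = 25). Settings were mean/SD 4/2.5, 4/3, 5/2.5 and 6/2, with correlation 0.5 to 0.7. The table gives the chance that normality is rejected and at least one value is at or below zero.

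| Assumed shape | Pooled, n = 100 | Single session, n = 25 |
|---|---|---|
| Normal | 2–15% | 1–6% |
| Right skew 0.5 | 0–43% | 0–13% |
| Right skew 1.0, at 4/3 | 85–91% | about 35% |
| Left skew 0.5 | 24–44% | 7–14% |
| Left skew 1.0 | 51–94% | 26–38% |
| t, 5 df | 28–53% | 11–21% |

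A separate run under skew 1.0 put the rejection rate alone at 67–92% pooled and 31–41% for a single session. Under the skewed shapes, single-session testing thus triggers roughly half as often or less. The pooled test also ignores clustering: with truly normal data it rejects 7.5% of the time at correlation 0.5 and 14.9% at 0.7.

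**5. Cost if values at or below zero are deleted.**

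*Gaussian fit after deletion.* A true 1.0-point effect is estimated as 0.84–1.00. The lowest value is for normal data at 4/3 and correlation 0.5, a shape that seldom triggers the gamma branch. Under right skew 1.0 at 4/3 it is 0.88–0.92. These figures show the effect of deletion on a Gaussian estimate, not on the gamma path.

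*Gamma fit after deletion.* Take mean/SD 4/3, correlation 0.6 and a 2-point effect. For the full-data Gaussian model:

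- within-patient variance = 9 × (1 − 0.6) = 3.6
- variance of the interaction estimate = 4 × 3.6/25 = 0.576, so SE = 0.759
- 2/0.759 = 2.64; residual df = 100 − 25 − 3 = 72, critical value 1.99
- power ≈ Φ(2.64 − 1.99) = Φ(0.65) ≈ 74%

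Simulation agrees (74–75%). The gamma mixed model after deletion gave 37–51%. The plan names no link function, and this range would change with the link, the shape and the fitting method.

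**6. Does the proposed model hold up?** The Gaussian random-intercept interaction test on 25 patients kept two-sided type I error at 4.8–5.2% under the shapes in step 4.

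**The case against.** The strongest reply is that no failure is shown. The section reports a finished analysis, and a gamma fit on values at or below zero fails visibly. If the report is accurate, BA-FMD was analysed as normal, or was all positive, or was altered without saying so. Only the third is a problem, and nothing in the documents points to it. The high probabilities in step 4 rest on one unstated choice, a single pooled test. All of this stands. It makes the point minor and rules out a headline probability. It also limits the remedy: where gamma was fitted to values that were all positive, the stated rule worked and no re-fit is called for. It does not remove the gap, because the rule can still lead to a model that does not accept the outcome.

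Some stronger readings are tempting and are not supported:

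- A reader might infer that the BA-FMD analysis failed or used deleted data. The documents do not say how BA-FMD was classified or whether any value was at or below zero.
- A reader might take the percentage change to be from the pre-treatment visit, because a parenthesis in Outcome measurements, item 1, contrasts pre- with post-intervention. Values at or below zero would then be almost certain (above 99.9% among 50 changes if the mean change is 0 to 1 SD). That reading fits poorly with a model that has time as a factor, and nothing here relies on it.
- A reader might call BA-FMD the primary outcome. The documents do not name it so.
- Nitroglycerin-mediated dilation is affected only if it too is expressed as a percentage change, which is not stated.

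**Conclusion.** The point holds in conditional form and is minor. The rule has no exemption, a percentage change can be zero or negative, and the gamma model cannot accept such values; these three facts need no assumed numbers. Whether the conflict arose is unknown. Its chance depends on the assumed mean, SD and shape and, two- to four-fold in many settings, on the unstated normality check, so no single figure should be quoted. If it did arise and values were deleted, the bias seen in a Gaussian fit is modest, and the larger cost is the illustrative loss of power under the gamma fit. All simulated figures assume equal correlation between sessions.

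**What to change.** Analyse BA-FMD (and nitroglycerin-mediated dilation, if expressed as a percentage change) with a Gaussian linear mixed model on the percentage-point scale whatever its observed distribution. Keep the condition, time, interaction and random-intercept terms, and check the residuals. Keep gamma for strictly positive skewed outcomes such as oxidized LDL and the albumin/creatinine ratio.

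Because the section describes completed work, state which model was used for BA-FMD, how any value at or below zero was handled, and whether baseline means the resting diameter within the session. Only if gamma was used with such values deleted or shifted, re-fit with the Gaussian model, report both results and label the re-fit post hoc.

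The cost is one or two sentences, a residual check and at most one re-fit. The downside is some loss of efficiency if the residuals are clearly skewed.
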